7.2.2. Part A: Dose Escalation (Phase 1a)

By nature of being a dose-escalation study, data will be evaluated on an ongoing basis until the MTD is determined. Safety data, in particular AEs, will be the primary criteria for the dose escalation. No dose escalation can occur without prior discussion and agreement between the investigator, the Lilly study team, and the collaborator; the decision will be documented in writing.

Based on the ongoing safety reviews, modifications to the dose-escalation strategy or other design elements may be made via protocol amendment to ensure patient safety. No intrapatient dose escalation is permitted for any patient. Dose escalation may be ceased at any time based on available safety and PK behavior.

In Part A, study drugs for the LY3022855-plus-durvalumab and LY3022855-plus-tremelimumab combinations may be administered at the dose regimens shown in [Table JSCC.1](#) and

Table JSCC.2, respectively. Refer to Section 7.2.2.2 for further details on the planned dose-escalation method, proceeding from Cohorts D1a and T1a.

Table JSCC.1. Part A (Dose Escalation) Dose Regimens for the LY3022855-plus-Durvalumab Combination, by Cohort

Cohort	LY3022855		Durvalumab	
	Dose (mg)	Frequency	Dose (mg)	Frequency
D1a	25	QW	750	Q2W
	D1b ^a	25 Days 1, 8, and 15 of each cycle	750	Q2W
	D1c	25 Q2W	750	Q2W
D2a	50	QW	750	Q2W
	D2b ^a	50 Days 1, 8, and 15 of each cycle	750	Q2W
	D2c	50 Q2W	750	Q2W
D3a	75	QW	750	Q2W
	D3b ^a	75 Days 1, 8, and 15 of each cycle	750	Q2W
	D3c	75 Q2W	750	Q2W
D4a	100	QW	750	Q2W
	D4b ^a	100 Days 1, 8, and 15 of each cycle	750	Q2W
	D4c	100 Q2W	750	Q2W

Abbreviations: QW = weekly; Q2W = every 2 weeks.

Note: A cycle is defined as 28 days (4 weeks). QW refers to dosing on Days 1, 8, 15, and 22 of each cycle; Q2W refers to dosing on Days 1 and 15 of each cycle.

^a Enrollment to the Dnb cohort will occur only if ≥ 2 DLTs are observed after Cycle 1, Day 21 of the corresponding Dna cohort.

Table JSCC.2. Part A (Dose Escalation) Dose Regimens for the LY3022855-plus-Tremelimumab Combination, by Cohort

Cohort	LY3022855		Tremelimumab	
	Dose (mg)	Frequency	Dose (mg)	Frequency ^a
T1a	50	QW	75	Q4W
	T1b ^b	50 Days 1, 8, and 15 of each cycle	75	Q4W
	T1c	50 Q2W	75	Q4W
T2a	100	QW	75	Q4W
	T2b ^b	100 Days 1, 8, and 15 of each cycle	75	Q4W
	T2c	75 Q2W	75	Q4W
T3a	100	QW	225	Q4W
	T3b ^b	100 Days 1, 8, and 15 of each cycle	225	Q4W
	T3c	100 Q2W	225	Q4W
	T3d	75 QW	225	Q4W
T4a	100	QW	750	Q4W
	T4b	100 Q2W	750	Q4W

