7.2.4.1.1. Specific Adverse Events

Adverse events of special interest (AESIs) observed with durvalumab and/or tremelimumab include colitis; pneumonitis; alanine aminotransferase (ALT)/AST increases; hepatitis/hepatotoxicity; neuropathy/neuromuscular toxicity (that is, events of encephalitis, peripheral motor and sensory neuropathies, Guillain-Barré, and myasthenia gravis); endocrinopathy (that is, events of hypophysitis, adrenal insufficiency, hyperthyroidism, and hypothyroidism; type 1 diabetes mellitus); dermatitis; nephritis; and pancreatitis (or labs suggestive of pancreatitis-increased serum lipase or serum amylase); other inflammatory responses that are rare with a potential immune-mediated etiology include, but are not limited to, myocarditis, pericarditis, myositis/polymyositis, and uveitis. Refer to [Attachment 8](#) for details about and management of AESIs.

Guidelines for the management of immune-mediated, infusion-related, and non-immune-related AEs are shown in [Attachment 7](#).

Adverse events (both nonserious and serious) associated with study drugs may represent an immune-related etiology, which may be based on the mechanism of action of study drugs leading to T cell activation and proliferation. These irAEs may occur shortly after the first dose or several months after the last dose of treatment. Potential irAEs include immune-mediated enterocolitis, dermatitis, hepatitis, and endocrinopathies. Patients should be monitored for signs and symptoms of irAEs. In the absence of an alternative etiology (for example, infection or progressive disease), signs or symptoms of enterocolitis, dermatitis, pneumonitis, hepatitis, myocarditis, myopathy/polymyopathy and endocrinopathy should be considered immune related. Refer to [Attachment 7](#) for supportive care guidelines for immune-mediated reactions, including use of corticosteroids.

Based on observations from clinical trials with LY3022855, patients receiving study treatment should be closely monitored for signs of hepatic function impairment (for example, increases in transaminases, lactate dehydrogenase [LDH], bilirubin, coagulation disorders) and creatine kinase increases.

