Vital signs	X				X				X				
BP, temperature, RR, PR, and weight.
 
Vital signs (BP, RR, and PR only) to be measured around infusions as follows (allowable window ± 10 min):
 
Around each LY3022855 infusion: prior to, during (midway through), at the end, and 30 min after the end.
 
Around each durvalumab infusion (based on a 60-min infusion): within 30 min prior to, during (approx. 30 min after start of infusion), and at the end (approx. 60 min after start of infusion).
 
1-h Observation period after durvalumab infusion: at 30 and 60 min after the end of the infusion (90 and 120 min after start of infusion) for the first durvalumab infusion only, and for subsequent infusions as clinically indicated.
 
If the durvalumab infusion exceeds 60 min, monitoring of BP and PR should occur per the preceding principles or more frequently if clinically indicated.

ECOG performance status	X				X				X				
Pregnancy test (local)					X								Every 12 wk (± 7 d) after the first dose of study drug or according to local regulations or as clinically indicated, whichever is more frequent. Urine hCG or serum β -hCG.
ECG (local)													Additional ECGs to be obtained as clinically indicated.
Hematology (local)	X	X	X	X	X	X	X	X	X				Refer to Attachment 2 .
Serum chemistry (local) - safety labs for dosing	X	X	X	X	X	X	X	X	X				Refer to Attachment 2 . Results must be available and reviewed before administering study drug.
Serum chemistry (central)	X	X	X	X	X	X	X	X	X				Refer to Attachment 2 .
Urinalysis (local)	X				X				X				Refer to Attachment 2 . To be performed at Screening, at C1D1, and every 4 wk thereafter. Additional assessments as clinically indicated. Results need not be available before administering study drug.

LY3022855 plus Durvalumab Assessment (central or local laboratory indicated, if applicable)	Cycle 3 (Visit 3)				Cycle 4 (Visit 4)				Cycle 5 (Visit 5)				Comments Except for the Cycle 1, Day 1 visit, allowable windows are ± 3 days, unless otherwise indicated. On dosing days, all assessments to be performed preinfusion, unless stated otherwise.
	1	8	15	22	1	8	15	22	1	8	15	22	
Relative day within a 28-day cycle:	1	8	15	22	1	8	15	22	1	8	15	22	
Coagulation (local)													Refer to Attachment 2 . As clinically indicated.

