Abbreviations: AE = adverse event; BP = blood pressure; CnDn = Cycle n, Day n (for example, C1D1 = Cycle 1, Day 1); CK = creatine kinase; CT = computed tomography (scan); CTCAE = Common Terminology Criteria for Adverse Events; ECG = electrocardiogram; ECOG = Eastern Cooperative Oncology Group; EOI = end of infusion; hCG = human chorionic gonadotropin; IRR = infusion-related reaction; LVEF = left ventricular ejection fraction; LY = LY3022855; MDSC = myeloid-derived suppressor cell; MRI = magnetic resonance imaging; MUGA = multigated acquisition (scan); NCI = National Cancer Institute; PK = pharmacokinetic(s); PR = pulse rate; RR = respiration rate; T3 = triiodothyronine; T4 = thyroxine; TSH = thyroid-stimulating hormone; v4.0 = Version 4.0 of NCI-CTCAE.

- ^a No follow-up procedures will be performed for patients who withdraw informed consent unless he or she has explicitly provided permission and consent.

Continued Access Schedule for Combination Therapy: LY3022855 plus Durvalumab

Visit	Continued Access Treatment Period	Continued Access Follow-Up ^a	*90-Day Follow-Up visit (Visit 902) is only for durvalumab safety. Instructions
	501-5XX	901 (30 d) and 902* (90 d) (± 7 d)	
Procedure^b			
AE collection	X	X	CTCAE v4.0. Refer to Section 8.1.1 for reporting guidelines.
Pharmacokinetics and immunogenicity		X	If a patient experiences an IRR, collect blood samples for PK and immunogenicity analysis at the following time points: (1) as soon as possible after the onset of the IRR, (2) at the resolution of the IRR, and (3) 30 days after the IRR.
Administer LY3022855 and durvalumab	X		Refer to Table JSCC.1 for dose frequency of LY3022855 during Part A. For LY3022855 and durvalumab: Part A doses: Refer to Table JSCC.1 . Part B doses and dose frequencies to be determined; refer to Section 7.2.2.2 for information.

Abbreviations: AE = adverse event; CTCAE = Common Terminology Criteria for Adverse Events; IRR = infusion-related reaction; v4.0 = Version 4.0 of CTCAE.

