ECG (local)													Additional ECGs to be obtained as clinically indicated.
Hematology (local)	X	X	X	X	X	X	X	X	X				Refer to Attachment 2 .
Serum chemistry (local) - safety labs for dosing	X	X	X	X	X	X	X	X	X				Refer to Attachment 2 . Results must be available and reviewed before administering study drug.

LY3022855 plus Tremelimumab Assessment (central or local laboratory indicated, if applicable)	Cycle 3 (Visit 3)				Cycle 4 (Visit 4)				Cycle 5 (Visit 5)				Comments
	1	8	15	22	1	8	15	22	1	8	15	22	
Relative day within a 28-day cycle:	1	8	15	22	1	8	15	22	1	8	15	22	
Serum chemistry (central)	X	X	X	X	X	X	X	X	X		X		Refer to Attachment 2 .
Urinalysis (local)	X				X				X				Refer to Attachment 2 . To be performed at Screening, at C1D1, and every 4 wk thereafter. Additional assessments as clinically indicated. Results need not be available before administering study drug.
Coagulation (local)													Refer to Attachment 2 . As clinically indicated.
Thyroid function (central)	X				X				X				Refer to Attachment 2 . Free T3 and free T4 will be measured only if TSH is abnormal or if there is clinical suspicion of an AE related to the endocrine system.
Pancreas function (central)	X				X								Refer to Attachment 2 .
Tumor markers (local)	X				X				X				If applicable.
Pharmacogenetic sample													Refer to the laboratory manual. Collect once. Sample can be collected at any time, if not collected on C1D1.
Immunogenicity	X												If at any time a patient experiences an IRR, attempts to obtain a blood sample for immunogenicity analysis as close to the onset of the event as possible, at the resolution of the event, and 30 days following the event. A portion of the sample taken for immunogenicity testing may be used for PK analysis.
Myoglobin (local)								X					Refer to Attachment 2 . If serum CK Grade ≥ 2 , test for serum and urine myoglobin.
CTCAE v4.0 grading	X	X	X	X	X	X	X	X	X	X	X	X	Throughout study as needed. Refer to Section 8.1.1 for reporting guidelines.
Concomitant medications	X	X	X	X	X	X	X	X	X	X	X	X	Throughout study as needed.
LY3022855 administration	Refer to Table JSCC.2 for dose frequency during Part A.												For LY3022855 and tremelimumab: Part A doses: Refer to Table JSCC.2 .
Tremelimumab administration	X				X				X				

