Visit	Continued Access Treatment Period	Continued Access Follow-Up ^a	*90-Day Follow-Up visit (Visit 902) is only for tremelimumab safety. Instructions
	501-5XX	901 (30 d) and 902* (90 d) (± 7 d)	
Procedure ^b			
AE collection	X	X	CTCAE v4.0. Refer to Section 8.1.1 for reporting guidelines.
Pharmacokinetics and immunogenicity		X	If a patient experiences an IRR, collect blood samples for PK and immunogenicity analysis at the following time points: (1) as soon as possible after the onset of the IRR, (2) at the resolution of the IRR, and (3) 30 days after the IRR.
Administer LY3022855 and tremelimumab	X		Refer to Table JSCC.2 for dose frequency of LY3022855 during Part A. For LY3022855 and tremelimumab: Part A doses: Refer to Table JSCC.2. If the patient has reached Cycle 7 or beyond in the main study, prior to the start of the Continued Access period, the patient will continue to receive tremelimumab in the Continued Access period according to their most recent dosing in the main study; continue dosing every 3 cycles.

Abbreviations: AE = adverse event; CTCAE = Common Terminology Criteria for Adverse Events; IRR = infusion-related reaction.

^a Continued access follow-up Visit 901 begins 1 day after the patient and the investigator agree that the patient will no longer continue treatment in the continued access period and lasts approximately 30 days. Visit 902 occurs 90 days (± 7 days) after the patient and the investigator agree that the patient will no longer continue treatment in the continued access period. No follow-up procedures will be performed for a patient who withdraws informed consent unless he or she has explicitly provided permission and consent.

^b Efficacy assessments will be done at the investigator's discretion based on the standard of care.

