Attachment 2. Protocol JSCC Clinical Laboratory Tests

Clinical Laboratory Tests - Assayed by Local Laboratory (local or investigator-designated laboratory)

Hematology

Hemoglobin
Hematocrit
Erythrocyte count (RBC)
Leukocytes (WBC)
Neutrophils
Lymphocytes
Monocytes
Eosinophils
Basophils
Platelets
Mean corpuscular hemoglobin
Mean corpuscular hemoglobin concentration
Mean corpuscular volume

Serum Chemistry

Sodium
Potassium
Chloride
Bicarbonate
Total bilirubin
Alkaline phosphatase
Alanine aminotransferase (ALT)
Aspartate aminotransferase (AST)
Albumin
Total protein
Blood urea nitrogen
Creatinine
Glucose, random
Creatine kinase

Coagulation

aPTT
PT, INR

Urinalysis^a

Specific gravity
pH
Protein
Glucose
Ketones
Blood
Urine leukocyte esterase
Nitrites
Bilirubin
Color and appearance

Serum or Urine Pregnancy Test (females only)

Myoglobin

Serum myoglobin
Urine myoglobin

Serologies

HIV screening

**Clinical Laboratory Tests - Assayed by Central Laboratory^b
(sponsor-designated laboratory)**

Serum Chemistry

Sodium
Magnesium
Potassium
Calcium
Chloride
Bicarbonate
Total bilirubin^c
Alkaline phosphatase
Alanine aminotransferase (ALT)
Aspartate aminotransferase (AST)
Gamma-glutamyl transpeptidase (GGT)^d
Albumin
Total protein
Blood urea nitrogen
Creatinine
Uric acid
Glucose, random
Creatine kinase

Thyroid Function

Thyroid-stimulating hormone
Free T3
Free T4
Isoenzymes
Alkaline phosphatase isoenzymes
Total creatine kinase
Creatine kinase isoenzymes
Total LDH
LDH isoenzymes

Pancreas Function

Amylase
Lipase

Abbreviations: aPTT = activated partial thromboplastin time; HIV = human immunodeficiency virus; INR = international normalized ratio; LDH = lactate dehydrogenase; PT = prothrombin time; T3 = triiodothyronine; T4 = thyroxine; ULN = upper limit of normal.

^a Microscopy should be used as appropriate to investigate WBCs and use the high power field for RBCs.

^b Results will be confirmed by the central laboratory at the time of initial testing.

^c If total bilirubin $\geq 2 \times$ ULN (and no evidence of Gilbert's syndrome), fractionate into direct and indirect bilirubin.

^d At baseline and as clinically indicated.

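### Scheduled safety labs drop to Day 1 only in Cycle 5 and are absent from Continued Access, although dosing continues and the chemistry row asks for results before study drug

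*Protocol*

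**What the plan says.** Attachment 1 of the protocol has a row titled "Serum chemistry (local) - safety labs for dosing" in both the durvalumab and the tremelimumab on-treatment schedules. Its comment reads "Results must be available and reviewed before administering study drug". The comment sits on the local chemistry row only; the hematology row just points to Attachment 2. The local chemistry panel in Attachment 2 includes ALT, AST, total bilirubin and creatine kinase (CK).

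On dosing, Section 7.2.2 says "QW refers to dosing on Days 1, 8, 15, and 22 of each cycle". Other cohorts receive LY3022855 on Days 1, 8 and 15, or on Days 1 and 15. Durvalumab is given on Days 1 and 15, and the schedule marks it on both days in Cycle 5.

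After study completion, the table headed "Continued Access Schedule for Combination Therapy: LY3022855 plus Durvalumab" has three procedure rows: AE collection, PK and immunogenicity, and "Administer LY3022855 and durvalumab". The tremelimumab counterpart has the same first two rows and "Administer LY3022855 and tremelimumab". Footnote b in each table leaves efficacy assessments to standard of care. It does not mention safety laboratory tests.

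Section 7.2.4.1.1 states that "patients receiving study treatment should be closely monitored for signs of hepatic function impairment", and it asks the same for CK increases. Attachment 7 sets hold, resume and stop rules that act on CK and AST values in patients without symptoms.

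**The concern.** The number of scheduled draws does not taper. It falls from four per cycle to one and then rises to two. No text explains why Cycle 5 should be lighter than every later cycle, and the row concerned is the one meant to inform dosing. The tremelimumab schedule marks central chemistry on Cycle 5 Day 15 but leaves local chemistry and hematology blank that day, which suggests a slip rather than a decision.

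Enzyme elevations are a recognised laboratory finding with LY3022855. Section 5.1.2 reports raised AST in 19 of 64 monotherapy patients (29.7%) and raised CK in 17 of 64 (26.6%), mostly Grades 1 and 2, and one Grade 4 rhabdomyolysis with acute renal failure. A rise without symptoms shows only on a blood test. If no test is scheduled, the Attachment 7 rules have nothing to act on until the next draw or until a clinical prompt leads to one.

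There is also a consequence for the analysis. Some CK and transaminase elevations meet the DLT criteria in Section 7.2.2.1. After Cycle 1 these count as dose-limiting equivalent toxicities (DLETs), and DLETs enter the Part B safety review rule in Section 7.2.3 (33% or more of a cohort, with at least 6 patients enrolled). Sparser testing before study completion could delay their detection.

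**Working it through.** There is no planned figure to reproduce. The check sets scheduled draw days against infusion days.

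**Draw days.** In the durvalumab table for Cycles 3 to 5, the local chemistry, hematology and central chemistry rows each have 12 day cells, with the first nine marked and the last three blank. That gives Days 1, 8, 15 and 22 in Cycles 3 and 4, and Day 1 in Cycle 5. The Cycle 6-n table marks Days 1 and 15. In the tremelimumab schedule, local chemistry and hematology follow the same pattern, while central chemistry is also marked on Cycle 5 Day 15. Draws per cycle for Cycles 3, 4, 5 and 6 are therefore 4, 4, 1, 2.

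**Infusions without a scheduled local draw** (infusion days minus draw days):

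| Period | Draw days | LY3022855 weekly | LY3022855 Days 1, 8, 15 | LY3022855 every 2 weeks | Durvalumab |
|---|---|---|---|---|---|
| Cycles 3, 4 | 1, 8, 15, 22 | 0 of 4 | 0 of 3 | 0 of 2 | 0 of 2 |
| Cycle 5 | 1 | 3 of 4 (Days 8, 15, 22) | 2 of 3 (Days 8, 15) | 1 of 2 (Day 15) | 1 of 2 (Day 15) |
| Cycle 6-n | 1, 15 | 2 of 4 (Days 8, 22) | 1 of 3 (Day 8) | 0 of 2 | 0 of 2 |
| Continued Access, per 28 days | none | 4 of 4 | 3 of 3 | 2 of 2 | 2 of 2 |

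Tremelimumab is given on Day 1 of a cycle, so its own on-treatment infusions do have a scheduled draw. The Cycle 5 gap in that schedule affects LY3022855.

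**Length of the gap.** Cycle 5 Day 1 to Cycle 6 Day 1 is 28 days, against 7 days in Cycles 3 and 4 and 14 days from Cycle 6. The ±3-day visit window does not close it: 28 − 3 − 3 = 22 days at the shortest. In the tremelimumab schedule, the central sample on Day 15 also measures CK, ALT and AST, so the gap in those values is 14 days there. The 28-day gap still applies to local chemistry and hematology, and the results-before-dosing comment is on the local row.

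**Rules against tests.** Attachment 7 has both drugs held and a diagnostic evaluation done for asymptomatic Grade 2 or Grade 3 CK, with a further split at 8 × ULN within Grade 3. It has LY3022855 held for isolated asymptomatic Grade 3 AST up to 8 × ULN. These rules start from a laboratory value. On the uncovered days above, no scheduled local draw supplies one.

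**Percentages quoted.** 19/64 = 29.7%; 17/64 = 26.6%. They show that enzyme elevations are common on LY3022855 alone. They do not show how many would first appear in Cycle 5 or later, because the documents give no onset times.

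**The case against.** The comment on the chemistry row can be read as applying only where a draw is scheduled: if blood is taken, read the result before dosing. On that reading, an infusion day with no draw breaks no rule. This is a fair reading, and Cycle 6-n, which leaves weekly Days 8 and 22 without a draw, is consistent with it. It does not explain why Cycle 5 has fewer draws than Cycle 6, and it says nothing about Continued Access.

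The protocol also has other routes to a test. Attachment 1 allows assessments whenever clinically required, Section 7.2.4.1.1 imposes a general duty of close monitoring, and Attachment 7 asks for weekly CK testing once CK is raised. These stand, but they help less with a silent rise. The first needs a clinical prompt, the second gives no frequency, and the third starts only after an elevation has been found.

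A reader might infer more than the documents support:

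- **That the hold rules cannot operate.** They can, from the Cycle 5 Day 1 and Cycle 6 Day 1 draws and from any unscheduled test.
- **That blood-count hold rules are disabled.** Attachment 7 has no rule specific to blood counts, only general grade-based rules for non-immune events.
- **That the Part B review rule is weakened in Continued Access.** That period begins after study completion, when the primary and secondary objectives have been met (Sections 6.2.1 and 6.2.2). The rule pauses Part B accrual, so by then it has nothing to act on.
- **That the monotherapy percentages measure what would be missed.** Most elevations were Grade 1 or 2, and isolated asymptomatic Grade 2 AST leads to continued dosing under Attachment 7.

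Finally, table cells read from a PDF can shift. In the durvalumab Cycles 3 to 5 table, the imaging mark falls on Cycle 4 Day 15, although the stated 8-week interval points to Day 22. The Cycle 5 blanks agree across three rows in one schedule and two in the other, and the durvalumab dosing row in the same table is placed correctly, so they are probably real.

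**Conclusion.** The point holds as an inconsistency in the schedule with a safety consequence. Cycle 5 has one scheduled local draw, below both the four before it and the two after it. That leaves between half (1 of 2) and three quarters (3 of 4) of LY3022855 infusions, and the Day 15 durvalumab infusion, without one. From Cycle 6, weekly cohorts lack a draw on Days 8 and 22, and the Days 1, 8, 15 cohorts lack one on Day 8. In Continued Access no infusion has a scheduled safety test. The supported consequence is that an asymptomatic CK or AST rise could be missed or found late and, before study completion, that a DLET could be detected late. The number of patients affected cannot be estimated from the documents. The conclusion assumes that the Cycle 5 blanks stand in the source table as they do in the text, and that no separate instruction outside these documents assigns laboratory tests to Continued Access.

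**What to change.** Reconcile three things, with the sponsor setting the testing frequency:

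1. The Cycle 5 local chemistry and hematology cells in both schedules with Cycles 3-4 and Cycle 6-n. Include the durvalumab central chemistry row and the isolated Day 15 central chemistry mark in the tremelimumab schedule.
2. The results-before-dosing comment with every infusion day that has no draw, including weekly Days 8 and 22 from Cycle 6. State whether it applies to each infusion or only to days with a scheduled draw.
3. The two Continued Access tables with Attachment 7 and Section 7.2.4.1.1, by stating which safety laboratory tests apply while dosing continues.

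The work is an edit to the schedule tables. The burden is at most a few routine blood draws on days when patients already attend for infusion.
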